#### 6.5. Visit Windows

Data will be tabulated and analyzed per the visit as recorded in the electronic case report form (eCRF).

Data collected at unscheduled visits will be included in by-subject listings and figures, but no assignment to a scheduled visit will be made for the purposes of by-visit summary tabulations. However, unscheduled visits will be considered for any categorical shifts summaries (e.g. shifts from baseline to 'worst' post-baseline value).

For patients who discontinued treatment, the time window for AEs, PD (ALA/PBG/ALAS1), attack and hemin use will be up to 28 days from the last dose.

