### 6.6. Interim Analyses

Interim analyses will be performed to support regulatory activities and publications. These analyses will be descriptive in nature and will not involve any formal hypothesis testing.

For an interim analysis, as this study will be ongoing, a cut-off approach will be implemented to ensure data quality. The interim analysis will include data entered on or prior to a pre-specified cutoff date. For assessments with starting/end dates (e.g., Exposure, AEs, medical history, medications), the starting date will be compared to the pre-specified cut-off date.

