#### 7. STATISTICAL METHODOLOGY

### 7.1. Patient Disposition

Patient disposition will be summarized and include the total number and percentage of patients in the following categories:

- Enrolled Patients (signed informed consent and met eligibility)
- Treated Patients
- Completed Patients
- Safety Analysis Set
- PD Analysis Set
- PK Analysis Set

Summaries of the number and percentage who discontinued study treatment based upon primary reason for discontinuation (e.g. AE, Death, Lost to Follow-up, Physician Decision, etc.) will be presented. Summaries of the number and percentage who withdrew from study prematurely based upon primary reason for withdrawal (e.g. AE, Death, Lost to Follow-up, Physician Decision, etc.) will also be presented. Per patient data listings will be presented displaying the primary reason the patient discontinued treatment and/or went off study.

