### 7.5.2. Clinical Activity

Clinical activity of ALN-AS1 will be assessed by the number of porphyria attacks and by the number of doses of hemin administered.

Analysis of Clinical Activity will be performed on the Safety Analysis Set.

**Porphyria attacks:** An attack will be defined as any event with preferred term="Porphyria" recorded on Adverse Event eCRF. Attacks which occur within the same date (i.e., end date of attack is the same date as start date of the next attack) will be counted as one attack. When collapsing attacks that occurred on the same date, the following rules will be applied for severity and location:

- 1. Severity will be assigned the maximum severity among the records.
- 2. Location will be assigned 'hospital' if  $\geq 1$  attack with location=hospital. Location will be assigned 'outpatient' if  $\geq 1$  attack with location=outpatient Location will be assigned 'home' if all the records state location=home. Location will be assigned 'other' if all the records state location=other.

The number of porphyria attacks during the treatment period (attacks with start dates on or after date of first dose) will be summarized. Annualized attack rate (AAR) per patient will be calculated as the total number of porphyria attacks divided by the total person-days at risk and multiplied by the total number of days in a year (365.25). Person-days at risk will be defined as: (date patient went off study – date of first dose+1). For an interim snapshot, the person-days will be defined by date of the first dose until the minimum of the date of the interim snapshot cut-off date or date the patient went off study. For calculation of AAR, only records with non-missing start and stop dates will be considered.

Porphyria attacks will be summarized separately in each subgroup:

- 1. Composite attacks: Attacks requiring hospitalization, urgent health care (i.e. outpatient clinic, Emergency Department, etc.) or IV hematin at home.
- 2. Attacks requiring hospitalization
- 3. Attacks requiring urgent health care (i.e. Outpatient)
- 4. Attacks required treatment with IV hematin at home
- 5. Attacks not treated with IV hematin at home
- 6. All attacks

For each subgroup, the total number of events, total person-years (total days/365.25), mean rate (total number of events/total person-years) and SEM will be presented for each study group. The

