SEM will be calculated using Cochran's estimate of SEM for weighted mean [1]. Attacks for each subgroup will display the rates separately for each phase of study: run-in (ALN-AS1-001 study) and treatment phase (ALN-AS1-002). A tabular summary of percentage change (%) in AAR rate from run-in to treatment phase will be also calculated per cohort. In addition, a by-patient listing will summarize the porphyria attacks in each of the subgroups. An exploratory analysis of AAR based on 6 months of givosiran dosing and beyond 6 months may be explored.

In addition, clinical activity will be assessed by duration and severity of attack (mild/moderate/severe). Reduction from run-in period (ALN-AS1-001 study) in composite to all attacks ratios will be assessed.

Hemin: Dosing with hemin will be summarized for doses during the treatment period (hemin start dates on or after the first dose of givosiran in this study). Hemin dosing will be identified as medication with standardized medication terms such as 'hematin', 'haem arginate' or 'hemin'. Annualized rate of hemin dosing will be summarized in the same manner as porphyria attacks (i.e., mean rate, SEM, person-years, total events). For the calculation of annualized rate of hemin, only records with non-missing start and stop dates will be considered. These summaries will also be presented in the same manner (i.e. separately for each cohort displaying results from each phase of study: run-in (ALN-AS1-001 study) and treatment phase (ALN-AS1-002). An exploratory analysis of Annualized rate of hemin dosing based on 6 months of givosiran dosing and beyond 6 months may be explored.

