#### 6.5. Visit Windows

Data will be tabulated and analyzed per the visit as recorded in the electronic case report form (eCRF).

For summaries based upon Intended-Dose Period, the following rules will be used:

- Data collected at scheduled visits (e.g. ALA, PBG, etc.) will be displayed if the collection was during the intended dose period (i.e., first date of intended dose ≤ collection date ≤ last date of intended dose)
- Data not collected at scheduled visits (e.g. AEs, attack, hemin) will be summarized if the start date was during the intended dose period (i.e., first date of intended dose ≤ start date ≤ last date of intended dose)

Data collected at unscheduled visits will be included in by-subject listings and figures, but no assignment to a scheduled visit will be made for the purposes of by-visit summary tabulations. However, unscheduled visits will be considered for any categorical shifts summaries (e.g. shifts from baseline to 'worst' post-baseline value).

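### For patients who stop treatment, SAP 6.5 ends attack and hemin counting 28 days after the last dose, but 7.5.2 runs person-days at risk to off-study or interim cut-off

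*SAP*

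**What the plan says.** The file holds three SAP texts. The conflict lies within one of them, the text that closes with the signature pages for VV-CLIN-003053 v1.0.

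- **Section 6.5, Visit Windows.** A limit is set for those who stopped treatment: "the time window for AEs, PD (ALA/PBG/ALAS1), attack and hemin use will be up to 28 days from the last dose".
- **Section 7.5.2, Clinical Activity, final analysis.** "Person-days at risk will be defined as: (date patient went off study", minus the first dose date, plus 1. The attacks counted are those starting on or after the first dose. No end date is given.
- **Section 7.5.2, interim snapshot.** Time at risk stops at cut-off, unless the patient left the study sooner: "the person-days will be defined by date of the first dose until the minimum of the date of the interim snapshot cut-off date".
- **Section 7.5.2, Hemin.** "Annualized rate of hemin dosing will be summarized in the same manner as porphyria attacks".
- **Section 7.5.2, use of the rates.** "A tabular summary of percentage change (%) in AAR rate from run-in to treatment phase will be also calculated per cohort".
- **Section 7.1, Patient Disposition.** Stopping treatment and leaving the study are summarized separately, with a listing "displaying the primary reason the patient discontinued treatment and/or went off study".

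The other two SAP texts have no 28-day limit in 6.5. In VV-CLIN-002514, for example, the only restriction there on such data concerns the intended dose period: "Data not collected at scheduled visits (e.g. AEs, attack, hemin) will be summarized if the start date was during the intended dose period". The person-days definition in 7.5.2 is the same in all three texts.

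**The concern.** An annualized rate needs its events and its time at risk to cover the same interval. Section 7.5.2 taken alone meets that: events and person-days both run to off-study. The 28-day sentence in 6.5 shortens the event window for discontinuers, and nothing in 7.5.2 shortens the person-days to match. Because 7.1 treats the end of treatment and the end of study as different events, the two dates can be far apart.

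Two programmers could therefore derive different attack and hemin rates from the same data. One who follows both sections to the letter obtains rates that can only be equal to or lower than the matched rates. That enlarges the apparent reduction from run-in, so the error favours givosiran. The rates may also be used before the study ends, since 6.6 says "Interim analyses will be performed to support regulatory activities and publications".

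**Working it through.** The SAP states no expected rate, number of discontinuers or power, so there is no planned figure to reproduce. The check applies the SAP's own formulas to assumed cases.

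**Inputs from the SAP**
- Per-patient rate = events ÷ person-days × 365.25 (7.5.2).
- Group rate = total events ÷ total person-years (7.5.2).
- Event window for discontinuers: to last dose + 28 days (6.5).
- Person-days: to off-study, or to cut-off if earlier (7.5.2).
- Up to 16 patients; treatment up to 36 months; post-treatment visit at month 39 or 42 (section 2).

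**Assumptions, because the SAP gives no values**
- One month = 30.4375 days, and the event rate is constant over time.
- Last dose at month T after the first dose.
- Gap from last dose to off-study of 28 days, 3 months (91.3 days) or 6 months (182.6 days).
- *Discontinued treatment* means premature stopping, as in 7.1.

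**Step 1: one patient.** Events accrue over T × 30.4375 + 29 days (28 days plus the 1 in the formula). Person-days are T × 30.4375 + gap + 1. The literal rate divided by the matched rate is

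(T × 30.4375 + 29) ÷ (T × 30.4375 + gap + 1)

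| Last dose | Gap 28 days | Gap 3 months | Gap 6 months |
|---|---|---|---|
| Month 6 | 1.000 | 211.6/274.9 = 0.770 | 211.6/366.2 = 0.578 |
| Month 12 | 1.000 | 394.2/457.6 = 0.862 | 394.2/548.9 = 0.718 |
| Month 24 | 1.000 | 759.5/822.8 = 0.923 | 759.5/914.1 = 0.831 |

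For gaps of 3 to 6 months the patient's rate is 23–42%, 14–28% and 8–17% too low in the three rows. Example: 3 attacks in the window, last dose at month 6, off study at month 9. The matched rate is 3 × 365.25 ÷ 211.6 = 5.18 per year; the literal rate is 3 × 365.25 ÷ 274.9 = 3.99. With no event in the window the rate is 0 either way.

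**Step 2: final group rate.** Take 16 patients, of whom k stop at month 6 and the others stay 39 months (1187.1 days). The shortfall is

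1 − [(16 − k) × 1187.1 + k × 211.6] ÷ [(16 − k) × 1187.1 + k × (182.6 + gap + 1)]

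For k = 3 and a 3-month gap: 1 − 16,066.7 ÷ 16,256.6 = 1.17%.

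| Discontinuers k | Gap 3 months | Gap 6 months |
|---|---|---|
| 1 | 0.35% | 0.85% |
| 2 | 0.74% | 1.78% |
| 3 | 1.17% | 2.81% |
| 4 | 1.65% | 3.94% |

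**Step 3: interim group rate.** Take all 16 patients first dosed 12 months before cut-off, so that the others contribute 366.25 days. With the same formula the shortfall is 1.10–2.64% for k = 1, 2.23–5.28% for k = 2 and 3.40–7.92% for k = 3.

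**Step 4: reduction from run-in.** Reported reduction = 1 − (1 − true reduction) × (1 − shortfall). For a true 50% and k = 3, the final analysis gives 1 − 0.5 × (1 − 0.0117) = 50.6% up to 1 − 0.5 × (1 − 0.0281) = 51.4%. The interim case gives 51.7% to 54.0%. A true 80% reads 80.2% to 80.6% at the final analysis with k = 3.

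**The case against.** The rules can be read in three ways: 6.5 limits both events and time, 7.5.2 governs both, or events follow 6.5 while time follows 7.5.2. Only the third biases the rate. Section 6.5 is a specific rule for a subset, and it is natural to read it as limiting both. Section 7.4 of the same SAP version supports an on-treatment intent: it ends exposure at the earliest of last dose + 27 days, cut-off and end of study. On this view the defect is mainly a missing cross-reference. That is a fair account of the likely intent, but it does not settle the text. Section 7.5.2 gives an explicit formula without exception, and nothing gives either section precedence.

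On size, the objection largely stands. Gaps, stopping times and numbers of discontinuers are all assumed, and early stoppers may leave within 28 days, in which case nothing changes. The large percentages concern one patient's rate. The group statistic to be tabulated is the pooled rate, where the final-analysis effect is at most about 4% in the cases shown. The upper interim figure needs three of 16 patients to stop at month 6 and all remain on study for six more months. The constant-rate assumption also matters: if attack rates change after treatment stops, the two possible remedies give different answers, and the shortfall above is measured against the window that ends at last dose + 28 days.

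Differences between SAP versions are not errors in themselves. Here they only suggest how the mismatch arose: a limit present in one version of 6.5, with 7.5.2 not adjusted to it.

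**Conclusion.** The inconsistency is real, and it is minor. Sections 6.5 and 7.5.2 set different ends of follow-up for the numerator and denominator of the same attack and hemin rates, and no text reconciles them. Read literally, the rates of discontinuers with at least one counted event and a gap above 28 days are too low, and the group reduction from run-in is slightly flattered. Under the assumptions above, the final pooled rate for 16 patients is too low by 0.4–3.9% for one to four discontinuers. A 12-month interim is affected more, by 1.1–7.9% for one to three. If either section is taken to govern both events and time, there is no mismatch. All analyses are descriptive, so no test or error rate is involved. What is at stake is the reproducibility and direction of planned outputs.

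**What to change.** State in 7.5.2 a single window for events and person-days, for both attacks and hemin, by one of two routes:

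- **(a)** For patients who discontinued treatment, end person-days at the earliest of last dose + 28 days, off-study date and cut-off date, and count events to the same date.
- **(b)** Count events and person-days to off-study or cut-off for everyone, and remove attack and hemin use from the 28-day sentence in 6.5.

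Cross-reference 6.5 and 7.5.2, and say which patients count as having discontinued treatment, in particular whether those who complete the planned treatment are included. Under (a), note that last dose + 28 days is one day later than the exposure end in 7.4 (last dose + 27 days), and either align the two or state that the difference is intended.

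The cost is one sentence or one deletion and one derivation. Under (a), discontinuers contribute fewer person-years and their rates may look less favourable. Under (b), off-treatment events enter the rates.

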#### 2. STUDY DESIGN

Study ALN-AS1-002 is an open-label, extension study designed to evaluate the long-term safety, clinical activity of givosiran in patients with AIP. The number of patients included up to 16 patients from Part C in the parent study ALN-AS1-001.

Eligible patients who completed Part C in the parent study either received the same dosing regimen as the pivotal Phase 3 study (e.g. 2.5 mg/kg every month) or had 1 or more dosing regimen changes across studies. The change in dosing regimen for a patient may occur due to emerging data and decisions from the Safety Review Committee (SRC). After a patient has completed 12 months of givosiran administration in this study (6 months in an every month dosing regimen), and where applicable country and local regulations and infrastructure allow, study procedures, including givosiran administration may take place at the patient's home by a healthcare professional. The expected duration of treatment for each patient is up to 36 months (3 years) followed by a post-treatment visits at either month 39/Early Termination visit or month 42.

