### 3. OBJECTIVES OF THE STUDY

# 3.1. Primary Objective:

• Evaluate the long-term safety and tolerability of givosiran in patients with AIP

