### 6.4. Study Groups

All tables and figures will be presented by the following study groups:

- Randomized treatment arm in the parent study/Current treatment arm (i.e., column for givosiran/givosiran vs. placebo/givosiran)
- Total (pooling regardless of randomized treatment arm in the parent study)

Summaries of key efficacy (e.g. PD and Clinical Activity) will also include study group:

• Intended Dose Group (i.e., givosiran 2.5 mg/kg monthly in ALN-AS1-002)

The following rules will be used:

- In analyses on PD measurements using the Intended Dose group, summaries at each postbaseline visit will be based on patients who are on 2.5 mg/kg at that visit.
- In analyses on clinical activity assessments (porphyria attacks and hemin use using the Intended Dose group, only events that occur between the first day of dosing and the last day of dosing with the intended dose regimen (2.5 mg/kg once monthly) are included.

An intended dose period will be defined as starting from the first dose of 2.5mg/kg Givosiran monthly.

Summaries of key safety (e.g. AEs) will also include study groups based upon initial dose in ALN-AS1-002:

- Initial dose of 2.5 mg/kg (monthly)
- Initial dose of 5 mg/kg (at any frequency)

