Summaries of AEs will consist of events which occur or worsen (including date/time when applicable) after the first dose of givosiran in this study. Note: Porphyria attacks are recorded on the AE eCRF, however they will not be reported as AEs but rather as an endpoint of clinical activity (see section 7.5.2); therefore, the term "AE" excludes porphyria events.

An overview of the frequency (percentage) of AEs including the total number of events will be tabulated (summaries such as but not limited to, the number of patients with at least 1 AE, the number of patients with at least 1 AE related to study drug, the number of patients with at least 1 serious AE [SAE], the number of patients who discontinued study drug to an AE). Separate tabulations will be generated by SOC and PT for all AEs, AEs by maximum severity, related AEs, related AEs by maximum severity, SAEs, discontinuation from study drug due to AEs, interruption due to AEs, and deaths. Patient listings will be generated separately for any patient who died, discontinued from study drug and reported any SAEs.

An additional set of AE outputs will also be generated by study groups defined by the initial dose of givosiran [i.e. Patients with an initial dose of 2.5 mg/kg (monthly) in ALN-AS1-002 and Patients with an initial dose of 5 mg/kg (at any time) in ALN-AS1-002].

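### The 28-day AE cut-off binds only patients who discontinued treatment, so the AE tables pool unequal post-dose windows and exempt no deaths, SAEs, AECIs or malignancies

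*SAP*

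**What the plan says.** All references are to the current SAP text, the first of the three versions in the file. The other two are superseded and carry no such cut-off.

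- **Section 6.5 (Visit Windows):** the rule for treatment discontinuers is that "the time window for AEs, PD (ALA/PBG/ALAS1), attack and hemin use will be up to 28 days from the last dose". No event type within AEs is exempted.
- **Section 7.4 (Safety Analyses):** "Summaries of AEs will consist of events which occur or worsen (including date/time when applicable) after the first dose of givosiran in this study". This is a lower bound only. The overview and the separate tabulations, including those for "SAEs, discontinuation from study drug due to AEs, interruption due to AEs, and deaths", are built on this definition. So are the AECI tables and the malignancy and acute renal failure tables.
- **Section 7.1 (Patient Disposition):** completed patients are a category of their own. The plan summarises the "number and percentage who discontinued study treatment based upon primary reason for discontinuation" and, separately, withdrawal from the study.
- **Section 2 (Study Design):** treatment lasts up to 36 months, "followed by a post-treatment visits at either month 39/Early Termination visit or month 42". The study takes "up to 16 patients from Part C in the parent study ALN-AS1-001".
- **Section 3.1 (Primary Objective):** "Evaluate the long-term safety and tolerability of givosiran in patients with AIP".

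**The concern.** A 28-day on-treatment window applied to everybody is an ordinary convention. Here the limit is written for one kind of patient only, and that kind is defined by something that happens after the first dose. Section 6.4 then puts discontinuers and completers in the same by-arm and Total columns, so an AE percentage in such a column has no single observation period behind it.

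The rule also makes no exception for the events that a long-term safety study most needs to count whenever they occur: deaths, SAEs, AECIs and malignancies. A malignancy starting two months after the last dose would be tabulated for a completer and not for a discontinuer. In a study this small, one such event visibly changes a table.

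**Working it through.** The study is descriptive and states no figure on this point to reproduce. The check sets the counting rules side by side and then does date arithmetic.

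**1. Which AEs count, by type of patient**

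| | Start of AE window | End of AE window | Source |
|---|---|---|---|
| Discontinued treatment | First dose in this study | Last dose + 28 days | 7.4, 6.5 |
| All others | First dose in this study | None stated | 7.4 |

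Section 7.1 separates stopping treatment from leaving the study, so a discontinuer may still be under observation after day 28. The cap can therefore remove collected data.

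**2. Length of the possible difference**

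Inputs: treatment up to month 36 and post-treatment visits at month 39 or 42 (Section 2); 28 days (Section 6.5). One month is taken as 365.25/12 = 30.44 days. *Assumption:* a discontinuer is followed after the last dose for as long as the planned post-treatment visits imply, that is 39 − 36 = 3 months or 42 − 36 = 6 months.

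- 3 months: 3 × 30.44 = 91.3 days; 91.3 − 28 = 63.3, about 63 days cut.
- 6 months: 6 × 30.44 = 182.6 days; 182.6 − 28 = 154.6, about 155 days cut.

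If discontinuers leave the study within 28 days of the last dose, the cut is 0 days.

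**3. Chance that a discontinuer loses at least one event**

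The SAP gives no event rate, so a range is assumed. With a constant rate r per patient-year, the chance is 1 − exp(−r × days cut / 365.25).

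| Assumed rate per patient-year | 63 days cut | 155 days cut |
|---|---|---|
| 0.1 | 1.7% | 4.1% |
| 0.3 | 5.1% | 11.9% |
| 1.0 | 15.9% | 34.5% |

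**4. Effect of one lost event on a table**

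With at most 16 patients, one patient is at least 1/16 = 6.25% of the Total column, and a larger share of a by-arm column. This holds only if the patient has no counted event in the same row already, because incidence counts each patient once.

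**The case against.** Several points on the other side stand.

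- **Completers' window is inferred.** A reader might infer that the SAP states completers' AEs are counted to end of study. It does not; it simply sets no limit for them. Section 7.4 also ends exposure for every patient at the earliest of last dose + 27 days, the analysis cut-off or EOS, so a window of about 28 days may have been meant for all. Alternatively, discontinued treatment might be meant to include planned completion. Section 7.1 points against that, because it lists completed patients separately and gives discontinuation reasons such as AE and death. If it were meant, no AE starting more than 28 days after the last dose would be tabulated for anyone, and the text would still need repair.
- **Events need not vanish from the report.** A reader might infer that late deaths and SAEs disappear. Section 7.4 plans listings for deaths, SAEs and most AECIs, and Section 7.1 reports death and AE as reasons. Section 6.5 does not window laboratory data, so the liver, lipase and eGFR tables can still show late abnormalities. Whether the cap also applies to listings is not stated. Malignancies have no dedicated listing.
- **The share lost is not known.** On the assumed follow-up, the cut is 69% (63.3/91.3) to 85% (154.6/182.6) of post-dose time. This is not a documented loss: Section 2 pairs month 39 with an early termination visit, so discontinuers may leave much sooner.
- **Two further inferences lack support.** The SAP does not say that patients often stop because of an AE; AE is one listed reason among several. The safety group labelled "Initial dose of 5 mg/kg (at any frequency" describes the initial dose, not the regimen at discontinuation, so it does not show that 28 days is wrong for particular patients.

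The choice of an on-treatment display is legitimate. What the objection does not remove is that Section 6.5 states a limit for one kind of patient and none for the rest.

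**Conclusion.** The point holds as a defect in a stated rule. As written, AE follow-up after the last dose ends at 28 days for discontinuers and has no stated end for others, and both share the same columns. Deaths, SAEs, AECIs and malignancies more than 28 days after stopping leave the summary tables for discontinuers only.

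The number of events affected cannot be derived and may be zero. The 63 to 155 days per discontinuer rest on an assumed 3 to 6 months of follow-up after stopping. The 6.25-point minimum shift rests on at most 16 patients and on no earlier counted event in the same row. The documents do not support a claim that the overall AE frequencies are materially biased. They support a claim that the frequencies lack a common window, and that serious late events may be left out of the tables for one group.

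**What to change.** 1. Tabulate deaths, SAEs, AECIs and malignancies through end of study for all patients, whether or not they discontinued treatment.
2. If an on-treatment AE table is kept, apply the same last-dose-based window to completers and discontinuers and label the table as on-treatment.
3. State the upper limit of the AE window in Section 7.4, bring Section 6.5 into line with it, and say whether any limit applies to listings.

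The cost is a change of SAP wording and one extra set of AE tables. No additional data collection is proposed. The reported frequencies may become slightly less favourable.
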